Kaplan-Meier techniques will be used to estimate disease-free/chronic GvHD-free survival at day 180. When estimable, additional summary statistics will include the median, minimum, maximum, the 25th and 75th percentiles along with the number of events and censored observations. Kaplan-Meier plots with descriptive summary statistics will be presented along with the number of patients at risk at various time points.

(vii) *Disease status for the following diseases at 180 days:*

- a. Primary immune disorders as determined by CD3 T cell count \geq 500 cells/uL and normal levels of IgA and IgM at 180 days
- b. Haemoglobinopathies as determined by incidence of RBC transfusion independence (TI) and untransfused haemoglobin of \geq 8.5 g/dL at 180 days
Transfusion Independence (TI) is defined as not having received packed red blood cell transfusions for the previous 8 weeks.
- c. Fanconi Anemia as determined by RBC \geq 3,000,000 cells/uL, neutrophil count \geq 1500 cells/uL and platelet count \geq 150,000 at 180 days
- d. Leukemia as determined by relapse-free-survival (RFS) at 180 days

For a)-d) above, cumulative incidence or survival will be assessed within the patient subpopulation defined as having those diseases at baseline. Cumulative incidence events for a.)-c.) are defined from the time of transplant until the event criteria described is achieved. Competing risks for a.)-c.) include any non-recurrence mortality. Events for RFS are defined as time to relapse or death from any cause.

Cumulative incidence for a.)-c.) will be estimated using a Nelson-Aalen cumulative incidence function for each disease subtype. When estimable, additional summary statistics will include the median, minimum, maximum, the 25th and 75th percentiles of immune reconstitution, along with the number of events and censored observations. A cumulative incidence plot with descriptive summary statistics will be presented along with the number of patients at risk various time points.

Kaplan-Meier techniques will be used to estimate RFS in subjects with leukemia. When estimable, additional summary statistics will include the median, minimum, maximum, the 25th and 75th percentiles along with the number of events and censored observations. Kaplan-Meier plots with descriptive summary statistics will be presented along with the number of patients at risk at various time points.

6.4.3. Other Efficacy Analyses:

(i) Time to Relapse in Subjects with Leukemia

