- 14.2.7 Kaplan-Meier Parameter Estimates of Time to Disease-Free/Chronic-GvHD-Free Survival

- 14.2.8.1-3 Cumulative Incidence Function Parameters of Time to Recovery of Primary Immune Disorders as Determined by CD3 T Cell Count >500 cells/uL, and Normal Levels of IgA and IgM

- 14.2.8.2 Cumulative Incidence Function Parameter Estimates of Time to Recovery of Haemoglobinopathies as Determined by Incidence of RBC Transfusion Independence and Haemoglobin of >8.5 g/dL
- 14.2.8.3-3 Cumulative Incidence Function Parameter Estimates of Time to Recovery of Fanconi Anemia as Determined by RBC > 3,000,000 cells/uL, Neutrophil Count > 1500 cells/uL, and Platelet Count >150,000
- 14.2.8.4 Kaplan-Meier Parameter Estimates of Relapse-Free Survival in Subjects with Leukemia
- 14.2.8.5 Cumulative Incidence of Relapse in Subjects with Acute Leukemia
- 14.2.9 Cumulative Incidence Function Parameter Estimates of Time to Neutrophil Engraftment
- 14.2.10 Cumulative Incidence Function Parameter Estimates of Time to Platelet Engraftment
- 14.2.11 Graft Failures

- 14.2.12.1 Time to Any Grade Infection
- 14.2.12.2 Time to Grade 3 or Higher Infection
- 14.2.13.1 Kaplan-Meier Parameter Estimates of Overall Survival
- 14.2.13.2 Kaplan-Meier Parameter Estimates of Disease-Free Survival in Subjects with Non-Malignant Disease
- 14.2.13.3 Sensitivity Analysis: Kaplan-Meier Parameter Estimates of Disease-Free Survival, by Dosing Window
- 14.2.13.4 Kaplan-Meier Parameter Estimates of Relapse-Free Survival in Subjects with Malignant Disease
- 14.2.13.5 Sensitivity Analysis: Kaplan-Meier Parameter Estimates of Relapse-Free Survival, by Dosing Window in Subjects Dosed at 1×10^6 Cells/kg
- 14.2.13.6 Sensitivity Analysis: Kaplan-Meier Parameter Estimates of Relapse-Free Survival, by Dosing Window in Subjects Dosed at 1×10^6 Cells/kg or Above
- 14.3.1.1 Treatment-Emergent Adverse Events Summary
- 14.3.1.2 Treatment-Emergent Adverse Events Regardless of Relationship to Study Treatment by System Organ Class, Preferred Term, and Dose of BPX-501
- 14.3.1.3 Treatment-Emergent Adverse Events Related to Occurring After AP1903 Administration, by System Organ Class, Preferred Term, and Dose of BPX-501
- 14.3.1.4.1 Treatment-Emergent Adverse Events Regardless of Relationship to Study Treatment, by System Organ Class, Preferred Term, and Maximum Severity
- 14.3.1.4.2 Treatment-Emergent Adverse Events Occurring After AP1903 Administration, by System Organ Class, Preferred Term, and Maximum Severity

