- 14.2.8.1.1 Cumulative Incidence Function Parameters of Time to Recovery of Primary Immune Disorders as Determined by CD3 T Cell Count >500 cells/uL, and Lower Normal Levels of IgA and IgM
- 14.2.8.1.2 Cumulative Incidence Function Parameters of Time to Recovery of Primary Immune Disorders as Determined by Normal Range IgA
- 14.2.8.1.3 Cumulative Incidence Function Parameters of Time to Recovery of Primary Immune Disorders as Determined by Normal Range IgM
- 14.2.8.2 Cumulative Incidence Function Parameter Estimates of Time to Recovery of Haemoglobinopathies as Determined by Incidence of RBC Transfusion Independence and Haemoglobin of >8.5 g/dL
- 14.2.8.3.1 Cumulative Incidence Function Parameter Estimates of Time to Recovery of Fanconi Anemia as Determined by RBC > 3,000,000 cells/uL, RBC Transfusion Independence and Haemoglobin of >8.5 g/dL
- 14.2.8.3.2 Cumulative Incidence Function Parameter Estimates of Time to Recovery of Fanconi Anemia as Determined by Neutrophil Count > 1500 cells/uL

- 14.2.8.3.3 Cumulative Incidence Function Parameter Estimates of Time to Recovery of Fanconi Anemia as Determined by Platelet Count > 150,000 cells/uL
- 14.2.8.4 Kaplan-Meier Plot of Relapse-Free Survival in Subjects with Leukemia
- 14.2.8.5 Cumulative Incidence of Relapse in Subjects with Acute Leukemia
- 14.2.9 Cumulative Incidence Plot of Time to Neutrophil Engraftment
- 14.2.10 Cumulative Incidence Plot of Time to Platelet Engraftment
- 14.2.12.1 Time to Any Grade Infection
- 14.2.12.2 Time to Grade 3 or Higher Infection
- 14.2.13.1 Kaplan-Meier Plot of Overall Survival
- 14.2.13.2 Kaplan-Meier Plot of Disease-Free Survival in Subjects with Non-Malignant Disease
- 14.2.13.3 Sensitivity Analysis: Kaplan-Meier Parameter Estimates of Disease-Free Survival, by Dosing Window
- 14.2.13.4 Kaplan-Meier Plot of Relapse-Free Survival in Subjects with Malignant Disease
- 14.2.13.5 Sensitivity Analysis: Kaplan-Meier Parameter Estimates of Relapse-Free Survival, by Dosing Window in Subjects Dosed at 1×10^6 Cells/kg
- 14.2.13.6 Sensitivity Analysis: Kaplan-Meier Parameter Estimates of Relapse-Free Survival, in Subjects Dosed at 1×10^6 Cells/kg or Above
- 14.2.13.7 Sensitivity Analysis: Kaplan-Meier Parameter Estimates of Relapse-Free Survival, by Dosing Window in Subjects Dosed at 1×10^6 Cells/kg or Above

Listings:

- 16.2.1.1 Subjects Screening, Enrollment and Eligibility Criteria
- 16.2.1.2 Donor Screening and Eligibility Criteria
- 16.2.1.3 On-Study Duration

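### The Fanconi Anemia recovery endpoint does not require untransfused red-cell and platelet counts, and its definition disagrees with one of the planned figures

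*SAP*

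**What the plan says.** The endpoint is defined in SAP sections 3.2 and 6.4.2(vii)c. The protocol supplied (BP-404) does not define it. Section 6.4.2 reads: "Fanconi Anemia as determined by RBC \geq 3,000,000 cells/uL, neutrophil count \geq 1500 cells/uL and platelet count \geq 150,000 at 180 days". Section 3.2 gives the same three thresholds. Neither place puts a transfusion condition on any of the counts.

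The timing rule for the non-leukaemia disease-status items is: "Cumulative incidence events for a.)-c.) are defined from the time of transplant until the event criteria described is achieved". Deaths without recurrence are the competing event.

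Two other SAP definitions do carry a transfusion condition:

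- **Haemoglobinopathy, item (vii)b:** "Haemoglobinopathies as determined by incidence of RBC transfusion independence (TI) and untransfused haemoglobin of" at least 8.5 g/dL, with the explanation that "Transfusion Independence (TI) is defined as not having received packed red blood cell transfusions for the previous 8 weeks".
- **Platelet engraftment, section 6.4.3(iii):** a count of at least 20,000/µL, with seven days free of platelet transfusion.

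The planned outputs in section 7.1.1 differ among themselves:

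- **Table 14.2.8.3-3** follows the text: "Time to Recovery of Fanconi Anemia as Determined by RBC > 3,000,000 cells/uL, Neutrophil Count > 1500 cells/uL, and Platelet Count >150,000".
- **Figure 14.2.8.3.1** does not: "Time to Recovery of Fanconi Anemia as Determined by RBC > 3,000,000 cells/uL, RBC Transfusion Independence and Haemoglobin of >8.5 g/dL".
- **Figures 14.2.8.3.2 and 14.2.8.3.3** show neutrophils and platelets alone, each with a bare threshold. The neutrophil title, for example, is "Time to Recovery of Fanconi Anemia as Determined by Neutrophil Count > 1500 cells/uL".

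**The concern.** Recovery in Fanconi Anemia is read from blood counts, and transfusion raises two of the three counts used. Where the SAP wants the patient's own red-cell or platelet production, for haemoglobinopathy and for platelet engraftment, it says so and sets a look-back period. For Fanconi Anemia it does not, so a programmer who follows the text would accept a transfused value as meeting the criterion.

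The output list then gives a second account of the red-cell component. If the text and table are programmed as written and the figure as titled, the same patient can be recovered in one and not in the other. At stake are the recovery estimate for a small disease subgroup and the consistency of its table and figures.

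**Working it through.** The SAP states no figure to reproduce here. The check compares definitions and adds a little arithmetic.

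**1. Transfusion conditions side by side**

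| Item | Red-cell condition | Platelet condition |
|---|---|---|
| Haemoglobinopathy, 6.4.2(vii)b | None in previous 8 weeks; haemoglobin untransfused | Not applicable |
| Platelet engraftment, 6.4.3(iii) | Not applicable | None for seven days |
| Fanconi, 3.2 and 6.4.2(vii)c | None stated | None stated |
| Fanconi, Table 14.2.8.3-3 | None stated | None stated |
| Fanconi, Figure 14.2.8.3.1 (red cells) | Transfusion independence, plus haemoglobin >8.5 g/dL | Not applicable |
| Fanconi, Figure 14.2.8.3.3 (platelets) | Not applicable | None stated |

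**2. Does the result depend on how the event is timed?** The heading and the criterion refer to 180 days, while the event rule runs from transplant until the criteria are met. The SAP does not settle which governs.

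- *First attainment.* Section 4.4 puts laboratory visits on Days 0, 14, 30, 60, 100 and 180. Under the 8-week rule, a patient given red cells around Day 0 cannot qualify before 8 × 7 = 56 days, so Day 60 is the first visit that could count. The Fanconi criteria carry no such delay.
- *Day 180 status.* The 8-week rule would exclude a patient given red cells after 180 − 56 = Day 124. The 7-day rule would exclude one given platelets after 180 − 7 = Day 173. The Fanconi text excludes neither.

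Transfused values can count under both readings. Early transfusion matters much less under the second.

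**3. Direction.** Adding a condition can only remove qualifying visits. Any visit that satisfies the thresholds and the transfusion rule also satisfies the thresholds alone. So recovery under the present text is never later, and never in fewer patients, than under the stricter rule. Under first attainment, a patient who reaches the counts on transfusion and then dies is a recovery; under the stricter rule that patient could be a competing event.

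**4. Where exposure is greatest.** The composite needs all three counts, and its platelet threshold is 150,000 / 20,000 = 7.5 times the engraftment threshold, so it is less exposed. In a single-lineage figure one transfused value is enough. The platelet figure is exposed as titled. The red-cell figure is exposed only if its transfusion wording is removed to match the text.

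**5. Size per patient.** The number of Fanconi patients, n, is not stated. With no censoring, one patient wrongly scored as recovered moves the proportion by 1/n:

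- n = 5: 1/5 = 20 percentage points
- n = 10: 1/10 = 10 points
- n = 20: 1/20 = 5 points

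These values of n are assumptions. The documents give no rate of misclassification.

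**The case against.** The case for leaving this alone has several parts.

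**The figure title may be a slip.** Its wording on transfusion independence and haemoglobin repeats the haemoglobinopathy figure, 14.2.8.2, listed just before it. SAP section 7.1 lets titles change without a revision. A copying error is plausible, so the figure is weak evidence of what was intended. But the same section reserves documentation for true differences in method or data handling, and whether transfused values count is one. The gap in the text remains whichever way the title is corrected.

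**A rule may exist elsewhere.** Section 3.2 says these endpoints come from the BP-004 protocols, which are not among the documents. The SAP supersedes the protocols where they differ, but silence is not clearly a difference. A transfusion rule in BP-004 cannot be ruled out. If there is one, the remedy is to state it in the SAP.

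**The composite is hard to reach on transfusion.** This stands. A reader might infer that the endpoint can be met by support alone. The documents do not show that: three thresholds must be met, one of them neutrophils, and the platelet threshold is high.

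**Growth factor.** A reader might also extend the contrast to growth-factor-supported neutrophil counts. The documents do not support that. Neither the haemoglobinopathy item nor any Fanconi figure has a growth-factor condition, and the SAP's neutrophil engraftment definition has none either. No look-back period can be drawn from the SAP, and complete capture of growth-factor use is not confirmed.

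**Conclusion.** The point holds for red-cell and platelet transfusion. As written, the Fanconi endpoint accepts transfused values under either reading of its timing, and the omission can only add or advance recoveries. Separately, Figure 14.2.8.3.1 conflicts with the text and with Table 14.2.8.3-3 on the red-cell component.

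It is a minor point. Fanconi Anemia is one of four disease-specific items under a single secondary endpoint, the analysis is descriptive, and neither the primary EFS analysis nor its power is affected. The range of 5 to 20 points per misclassified patient rests on an assumed n of 20 down to 5, and on such a patient occurring at all. The finding does not reach growth factor, and it does not claim that transfusion alone can satisfy the three-lineage composite.

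**What to change.** In SAP sections 3.2 and 6.4.2(vii)c:

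- count the red-cell criterion only when no packed red cells were given in the previous 8 weeks, which is the SAP's existing transfusion-independence rule;
- count the platelet criterion only when no platelets were transfused in the previous 7 days, which is the existing platelet engraftment rule;
- leave the neutrophil criterion as it is.

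State whether the event is first attainment or Day 180 status. Apply the one definition to Table 14.2.8.3-3 and, lineage by lineage, to Figures 14.2.8.3.1 to 14.2.8.3.3. Decide whether the haemoglobin limit in the title of Figure 14.2.8.3.1 belongs to this endpoint, and either add it to the text or remove it from the figure.

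The cost is SAP wording and programming. Transfusion data are already planned for Listing 16.2.4.10, so no new data item is proposed. The downside is that recovery will be reached later or by fewer patients.

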6.5. Safety Endpoints

Data for adverse events (AEs), serious adverse events (SAEs), clinical laboratory parameters, vital signs, and physical examinations will be presented in subject listings, including assessments of abnormality and clinical significance, where applicable. Summaries will be prepared for key variables (detailed below) by study visit (where applicable) for all patients as well as by malignant/non-malignant disease status. No inferential statistical testing will be performed for safety variables.

Unless otherwise specified, safety analyses will be conducted primarily within the BPX-501 safety population. Additional safety listings will be provided focusing (i) on the subjects enrolled into the initial dose escalation portion of the study, and on the subjects enrolled into the study but who either (ii) did not receive HSCT, or who (iii) received HSCT but did not receive BPX-501. Only SAEs were collected prior to administration of BPX-501.

For the purposes of analysis, treatment-emergent adverse events will be defined as those AEs with onset or worsening date occurring on or after the date of infusion with BPX-501.

6.5.1. Adverse Events

Each verbatim adverse event (AE) term recorded during the study will be mapped to a system organ class and preferred term using MedDRA Dictionary version 18.0.

Study treatment-related adverse events will be defined as the adverse events for which the investigator indicates the relationship to study drug as possible, probable, or definite. Relatedness of AEs for patients treated with rimiducid will be assessed among those patients from the date of first dose of AP1903.

All summaries of AEs will present the number and percent of subjects reported events by system organ class and preferred term. If a subject has multiple occurrences of an AE, the subject will be counted only once for the respective AE category at the SOC or preferred term level.

At a minimum, the following AE tables will be summarized by SOC and preferred term:

- Number and percentage of patients with any AE
- Number and percentage of patients with AEs by maximum severity
- Number and percentage of patients with G3 or higher AEs
- Number and percentage of patients with serious AEs (SAEs)
- Number and percentage of patients with AEs leading to death

Summaries will be presented for all subjects as well as by type of disorder (e.g. malignant or non-malignant). If any of the proposed tables has very limited occurrence, only patient listings may be provided.

At a minimum, the following patient listings will be provided:

- All AEs
- All SAEs
- All AEs leading to death

Specific listings and tables for GvHD, infections, and neurological events will be provided. Neurological events will be categorized relative to basket of preferred terms curated against MedDRA version 21.0. Key coding differences between this list and the MedDRA version used for broader AE coding will be highlighted.

6.5.2. Laboratory Data

Individual clinical laboratory results (hematology and chemistry) will be presented in data listings.

Frequency tabulations of the number of normal and abnormal (low and high) records will also be summarized in shift tables showing the number and percentage of subjects with lab values in each classification at each post-baseline visit relative to baseline classification frequencies.

Listings of individual laboratory data, indicating any clinically significant or values out of the normal range will be produced.

6.5.3. Vital Signs

Vital signs are recorded at baseline and at different visits post-baseline. All individual vital signs results (systolic blood pressure, diastolic blood pressure, heart rate, respiratory rate and body temperature) will be presented in data listings. Visit-wise observed vital signs parameter values and changes from baseline will be summarized by study visit using descriptive statistics. Vital signs following HSCT infusion, BPX-501 infusion and AP1903 administration will be included.

6.6. Changes to Statistical Analysis Methods Planned in the Protocol

No major changes have been identified in this SAP when comparing to the protocol. Analysis populations have been further clarified. Cut-offs for certain analytes, e.g., T cell subsets relating to immune reconstitution, may have been changed in order to harmonize across BPX-501 protocols.

Prior versions of the protocol had referred to measuring progression-free survival or leukemia-free survival in subjects with leukemia. As BP-004 subjects were transplanted while in remission, and for consistency with other BPX-501 protocols, this endpoint has been appropriately renamed and corrected to relapse-free survival.

In several instances, the protocol mentioned that certain exploratory analyses will be summarized by BPX-501 dose, CD34+ cell dose in the allograft, $\gamma\delta$ T cell dose in the allograft, $\alpha\beta$ T cell dose in the allograft, ATG dosing, and conditioning regimen, among other parameters. Based on data availability or suitability, subgroup analyses and/or analyses accounting for each of these variables may not be provided for all such endpoints.

6.7. Additional Exploratory Analyses

Other exploratory subgroup analyses to characterize safety and efficacy activities for BPX-501 may be conducted. These additional exploratory analyses will be decided at the time of final data analysis.

Sparse PK sampling collected from patients that receive rimiducid will be used to determine the concentration time profile of rimiducid in plasma and summarized as described above. Rimiducid plasma concentration data collected from these subjects will be used as part of a population PK modeling and meta-analysis that will be presented in a separate document. Additional PK assessments may be performed as deemed appropriate.

In addition to the pharmacodynamic and translational analyses specified above, further exploratory analyses are planned and will also be presented in separate documents. These analyses include, among others, analysis of CD45RO/CD45RA/CD62L/CCR7, T cell diversity, and thymic function.

The following additional efficacy analyses were not specified in the protocol, but are being proposed in order to assess longer-term outcomes beyond 180 days and to harmonize with other

study protocols investigating the use of BPX-501. The analyses will be conducted in the ITT population, and, possibly, in the PP population as well.

- (i) Transplant-Related Mortality and Non-Relapse Mortality, defined earlier, at 1 year and 2 years from the time of HSCT. TRM and NRM at those time points will be estimated using a Nelson-Aalen cumulative incidence function.
- (ii) Overall Survival, defined as the time from HSCT to death due to any cause, at 180 days, 1 year and 2 years. Overall survival will be analyzed in all patients as well as stratified by disease subtype (malignant and non-malignant). Overall survival at those time points will be estimated using a Kaplan-Meier survival function.
- (iii) Disease-Free Survival, defined as the time from HSCT to disease recurrence or death, whichever occurs first, in subjects with non-malignant disease. DFS will be estimated at 180 days, 1 year and 2 years using a Kaplan-Meier survival function.
- (iv) Relapse-Free Survival, defined as the time from HSCT to disease relapse or death, whichever occurs first, in subjects with malignant disease. RFS will be estimated at 180 days, 1 year and 2 years using a Kaplan-Meier survival function.

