## 2 SYNOPSIS

Study Identifier(s)	BP-404 EudraCT #2016-003226-16
Aim of the Study	This is a Phase I/II study to evaluate the long-term safety of the infusion of BPX-501 gene-modified T cells after mismatched, T cell-depleted allogeneic transplantation and evaluate disease free survival at 1 and 2 years post-transplant
Study Design	
Open label, multi-centre, non-randomized, non-controlled long-term safety evaluation
 
Follow-up of all patients enrolled on BP-004 and treated with BPX-501 who are beyond Day 180 and have completed or discontinued the parent study.

Study Population	The patient population is identical to BP-004 as it is the long-term follow-up of those patients. Estimated enrolment up to 175 BP-004 patients.
Main Inclusion Criteria	
 
1. Signed written informed consent by the patient or the patient's guardian for children who are minors
 
2. Enrolled on BP-004 protocol, received BPX-501 infusion, completed or discontinued from the study, and are beyond Day 180.
 

Main Exclusion Criteria	
 
1. Lack of parents'/guardian's informed consent for children who are minors
 
2. Withdrawal from BP-004 study prior to BPX-501 infusion.
 

Dosage, Treatment Regimen, Route of Administration	
No BPX-501 infusions will be administered under this protocol.
 
Rimiducid to be given at 0.4 mg/kg weight (intravenous infusion) only in the setting of uncontrolled GVHD.

Locations (e.g. regions)	Italy, Saudi Arabia.
Primary Endpoint(s) with Time Point(s) of Assessment	Overall Survival and incidence of Disease-Free Survival in both malignant and non-malignant patients at 1 year and 2 years post-transplant. Relapse-Free Survival in malignant patients at 1 year and 2 years post-transplant.
Main Secondary Endpoint(s) with Time(s) of Assessment	Long-term safety for a total of 15 years from BPX-501 administration

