### **5 OBJECTIVES OF THE STUDY**

#### **5.1 Primary Objective**

Overall Survival and incidence of Disease-Free Survival in both malignant and non-malignant patients at 1 and 2 years post-transplant. Relapse-Free Survival in malignant patients at 1 year and 2 years post-transplant.

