## 7.2 Trial Design

The BP-004 Phase I trial design consisted of 3 different escalating doses ( $2.5 \times 10^5$ ,  $5 \times 10^5$ ,  $1 \times 10^6$  cells/kg recipient total body weight) in all patient populations and further escalation of 2 doses ( $2 \times 10^6$ ,  $4 \times 10^6$  cells/kg recipient total body weight) were evaluated in patients with malignant disease only.

Patients were enrolled at the recommended dose for a maximum of 175 pediatric patients total (for both phases), and the minimum active study follow-up for each patient was 180 days in protocol BP-004.

Patients enrolled on the BP-004 study who received BPX-501 T-cells and are beyond Day 180 will be requested to enroll on this long-term follow up protocol, regardless of whether they completed or discontinued from the parent study BP-004.

The follow-up time for evaluation for overall survival and disease-free survival in patients with malignant disease and patients with non-malignant disease will be 1 and 2-years post-transplant. Relapse-free survival in malignant patients will be evaluated at 1 and 2 years. Long term follow-up for survival and gene therapy safety will be 15 years after BPX-501 treatment.

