### **10.4.2 General Statistical Approach**

Descriptive statistics will be utilized to summarize overall survival, RFS, DFS, GvHD rates, clinical and biologic response and other measures of safety and toxicity in those patients who received rimiducid administration as well as for the whole population. The analysis population will be stratified by malignant and non-malignant indications.

Data per cohort will be presented, stratified according to the type of disorder, e.g. malignant or non-malignant.

All summary tables for quantitative parameters will display mean, standard deviation, median, range (minimum and maximum), as well as number of missing data, where relevant. All summary tables for qualitative parameters will display counts, percentages, and, number of missing data, where relevant.

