This Statistical Analysis Plan (SAP) is based on the BP-004 study protocol and is intended to provide the statistical methods and summaries for the analysis of the data arising from the clinical trial (Protocol BP-004, Italy Version 10.0, 2 April 2018; United Kingdom Version 7.0,c 2 April 2018). Once completing the initial 180-day follow-up period, subjects enrolled into the Italian version of the BP-004 protocol were enrolled into a follow-up protocol, BP-404. Analyses presenting data beyond Day 180 in this SAP may therefore pull data from all three protocol sources (Italy and United Kingdom BP-004; Italy BP-404). The analysis approaches and methods outlined in this document, if different from the respective protocols, will supersede those specified in the protocol.

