6. STATISTICAL METHODS AND DATA HANDLING

6.1. Analysis Populations

The following analysis populations are defined for the study:

(i) *Enrolled Population (EP)* – Defined as all patients who signed informed consent, were assessed for inclusion/exclusion criteria during the screening period, and who were considered eligible for enrollment and post-enrollment follow-up. This population will be used to present overall study disposition data and for summarizing the total number of patients screened and considered eligible for the study.

(ii) *HSCT Safety Population (HSP)* – Defined as all patients in the enrolled population (EP) who received Hematopoietic Stem Cell Transplantation (HSCT). Only SAEs were reported in subjects prior to receiving BPX-501. The HSP therefore represents the analysis population for certain analyses of SAEs as well as disposition and outcomes in subjects who did not go on to receive BPX-501 for any reason.

(iii) *BPX-501 Safety Population (BSP)* – Defined as all patients who received HSCT and went on to receive any dose of BPX-501. Unless otherwise specified, this will be the default primary safety analysis population.

(iv) *Intent-to-treat Population (ITT)* – Given that this is a single-arm study, a “Full Analysis Set” (FAS) population is proposed to serve as the ITT population from which to provide estimates of treatment effects in subjects receiving BPX-501. The FAS/ITT population includes all patients treated with HSCT who received BPX-501 at the dose of 1×10^6 cells/kg.

(v) *Per Protocol Populations (PP)* – Defined as all patients in the ITT/FAS analysis population who were infused with BPX-501 at the dose of at least 1×10^6 cells/kg within a dosing around Day 14 (+/- 4 days) or Day 21 (+/- 14 days) after HSCT. The primary and key secondary efficacy analyses may be repeated on the PP populations as a means of characterizing the robustness of any outcome results.

(vi) *Rimiducid Population (RP)* – Defined as all patients who received at least one dose of rimiducid for the treatment of acute or chronic GvHD.

(vii) *Rimiducid Pharmacokinetics Population (RPK)* – Defined as all patients who received at least one dose of rimiducid for the treatment of acute or chronic GvHD and have a plasma sample to measure rimiducid concentrations over time.

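### The SAP restricts 1- and 2-year OS, DFS, RFS and TRM/NRM to patients dosed at 1x10^6 cells/kg, while BP-404 specifies survival results for all BPX-501-treated patients, and the difference is not declared

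*SAP*

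**What the plan says.** **BP-404 protocol.** The Synopsis defines the study as "Follow-up of all patients enrolled on BP-004 and treated with BPX-501 who are beyond Day 180 and have completed or discontinued the parent study". Neither it nor the inclusion criteria (5.4) sets a dose limit. Section 5.1 gives the primary objective as "Overall Survival and incidence of Disease-Free Survival in both malignant and non-malignant patients at 1 and 2 years post-transplant", plus RFS in malignant patients at the same times. Section 10.4.2 asks for OS, RFS and DFS in rimiducid recipients "as well as for the whole population", and for data per cohort by type of disorder. On dose, section 7.2 says the "BP-004 Phase I trial design consisted of 3 different escalating doses": 2.5x10^5, 5x10^5 and 1x10^6 cells/kg in all populations. Two more levels, 2x10^6 and 4x10^6, were evaluated in malignant disease only.

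**SAP.** Section 2 says the SAP is based on the BP-004 protocol, may draw on BP-404 data beyond Day 180, and that its methods, "if different from the respective protocols, will supersede those specified in the protocol". Section 6.7 adds TRM/NRM, OS, DFS (non-malignant) and RFS (malignant) at 1 and 2 years, and states: "The analyses will be conducted in the ITT population, and, possibly, in the PP population as well". Section 6.1 (iv) reads: "The FAS/ITT population includes all patients treated with HSCT who received BPX-501 at the dose of" 1x10^6 cells/kg. Section 6.1 (v) draws PP from within that set. Section 6.1 (iii) separately defines the BPX-501 Safety Population (BSP) as patients transplanted and given any dose. Section 6.6 reports no major changes from the protocol.

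**The concern.** The same endpoints at the same times have two denominators: every treated patient in the BP-404 protocol, and one dose level in the SAP. A reader of the eventual report could not tell which one answers BP-404's primary objective. The patients outside the FAS include those given the lowest and the highest cell doses. The highest doses were given only in malignant disease, so the malignant OS estimate omits its highest-dose patients. A long-term follow-up of a gene-modified cell product should be able to state survival for everyone treated.

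**Working it through.** **The plan's own figures.** Neither document states a sample size rationale, power or precision for 1- or 2-year OS, DFS or RFS. SAP 4.2 gives power for day-180 EFS only. With rates of 88% and 91%, a 10% margin and one-sided 2.5%, the stated 91% (160 v 100) recomputes as 90.7-91.6%. The stated 84% (140 v 70) recomputes as 83.2-85.0% with pooled or Farrington-Manning variance, and as 81.1% unpooled. These figures do not bear on this point.

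**Who has a planned 1- and 2-year estimate.** This sets SAP 6.1 and 6.7 against the planned outputs in SAP 7.1.1 and the dose levels in protocol 7.2.

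| Patients | OS | DFS (SAP: non-malignant) | RFS (SAP: malignant) |
|---|---|---|---|
| 1x10^6, including any treated there during escalation | FAS | FAS | FAS |
| 2.5x10^5 and 5x10^5, non-malignant | none | none | not applicable |
| 2.5x10^5 and 5x10^5, malignant | none | not applicable | none |
| 2x10^6 and 4x10^6 (malignant only) | none | not applicable, by diagnosis | sensitivity outputs only |

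The sensitivity outputs are Table 14.2.13.6 and Figures 14.2.13.6 and 14.2.13.7, which cover 1x10^6 and above. OS (14.2.13.1) and DFS (14.2.13.2 and 14.2.13.3) have no all-dose version. TRM/NRM at 1 and 2 years falls under the same ITT sentence as OS. PP cannot restore other doses, because it is a subset of the FAS.

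**How many patients.** The documents give no counts by dose. SAP 4 says escalation was 3+3, so assume 3-6 patients at each of the four other levels.
- 4 x 3 = 12 and 4 x 6 = 24.
- 12/175 = 6.9% and 24/175 = 13.7%, taking 175 as the total for both phases (protocol 7.2).

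**How far the estimate could move.** With k patients outside the FAS and N treated, the all-dose estimate differs from the FAS estimate by (k/N) x d, where d is the survival difference between the two groups. Assume d = 10 to 20 points.
- Smallest: 12/175 x 10 = 0.69 points.
- Largest: 24/175 x 20 = 2.74 points.

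The FAS standard error, at an assumed 85% survival and ignoring censoring, is sqrt(0.85 x 0.15/(175 - k)).
- k = 12: sqrt(0.1275/163) = 2.80 points; 0.69/2.80 = 0.25 SE.
- k = 24: sqrt(0.1275/151) = 2.91 points; 2.74/2.91 = 0.94 SE.

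**Sensitivity to cohort structure.** If the two lower levels were escalated separately in malignant and non-malignant patients, which the documents do not say, there are six cohorts and k = 18-36 (10.3-20.6%). At k = 36 and d = 20 the shift is 36/175 x 20 = 4.11 points, against an SE of sqrt(0.1275/139) = 3.03, or 1.36 SE. The result that the shift is under one SE therefore depends on a single escalation.

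**The case against.** The strongest reply is that this SAP belongs to BP-004. Its primary endpoint is 180-day EFS. It calls longer-term results supportive (SAP 4), places the 1- and 2-year estimates among exploratory analyses that it says the protocol did not specify (6.7), and ties its final analysis to the last UK patient (5.2). Section 10.4.2 of the BP-404 protocol might then still govern BP-404's own report. This stands in part: the SAP reaches BP-404 only through its clause on the respective protocols together with its use of BP-404 data. It does not remove the conflict, because neither document says which population applies.

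A reader might infer that all dose-escalation patients drop out of BP-404's primary result. The documents do not support that. The FAS is defined by dose and not by phase, so escalation patients treated at 1x10^6 stay in, and the SAP never calls its 6.7 outputs BP-404's primary analysis. Nor is RFS estimated solely in the FAS, given the sensitivity outputs. The 2x10^6 and 4x10^6 patients are outside the SAP's DFS because of their diagnosis, not their dose.

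It would also be wrong to say that outcomes at other doses go unreported. Safety analyses default to the BSP. A deaths summary (14.3.2.8), mortality and death listings (16.2.6.4, 16.2.7.5) and a listing of OS, DFS and RFS (16.2.6.1.3) carry no stated dose limit. These show deaths and individual times, but they are not 1- and 2-year estimates.

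SAP 6.7 does say that OS covers all patients. That wording comes after the ITT sentence and is contrasted with disease strata, so it most naturally means all ITT patients. Finally, an FAS at the recommended dose is a legitimate choice for BP-004, and with a few patients per level a split by dose can only be descriptive.

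**Conclusion.** The point holds as a population mismatch that the plan neither resolves nor declares. As written, four of the five dose levels have no planned 1- or 2-year OS or TRM/NRM estimate. The two lowest also lack DFS (non-malignant) and RFS (malignant), and the two highest have RFS only as a sensitivity analysis. This part rests on the text alone.

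The numerical effect is probably modest: 12-24 of 175 patients and 0.7-2.7 points, under one SE. The cohort sizes, the survival difference and the 85% rate behind it are all assumptions, and separate escalation by disease type could take the extreme case above one SE. The case for change is that the reported denominator should be the one BP-404 specifies. The documents do not show that the FAS result would mislead.

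**What to change.** In SAP 6.7, add 1- and 2-year OS, DFS, RFS and TRM/NRM in the BPX-501 Safety Population, named as the estimates that answer BP-404's objective. Give the number of patients at each dose level and a descriptive split: below, at and above 1x10^6 cells/kg. Keep the FAS analysis beside them as the recommended-dose result. In SAP 6.6, record that the FAS population differs from the one in BP-404 section 10.4.2.

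The BSP matches BP-404's dose scope, not its enrolment list: it also holds patients who never reached Day 180 and UK patients. The FAS shares both features, so comparing the two isolates the dose filter.

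The cost is a few sentences and a re-run of a few tables and figures on a population already defined, with no new data. The downside is that the all-dose estimate mixes doses, which is why the FAS result stays beside it.
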